Title	Post-licensure observational safety surveillance study of quadrivalent meningococcal ACWY conjugate vaccine MenACWY-CRM (MENVEO [®]) in children 2 months through 23 months of age.
Protocol version identifier	V. 2
Date of last version protocol	11 AUG 16
EU PAS registry number	Not applicable.
Active substance	Not applicable.
Medicinal product	Not applicable.
Product reference	Not applicable.
Procedure number	Not applicable.
Marketing authorisation holder(s)	GlaxoSmithKline Biologicals S.A.
Joint PASS study	NO

Research question and objectives	To describe medical events that require emergency room visit or hospitalization in 6 months following MenACWY-CRM vaccination in children 2-23 months of age in a health maintenance organization (HMO) in the United States.
Country(ies) of study	United States
Author	[name], GSK
Marketing authorisation holder(s) details	GlaxoSmithKline Biologicals S.A [name]. Belgium
MAH contact person	[name] and Epidemiology R&D GSK Amsterdam, The Netherlands Email: PPD

Property of GlaxoSmithKline Biologicals S.A (hereafter referred to as GSK)

Confidential

May not be used, divulged, published or otherwise disclosed without written consent of GSK

2.0 LIST OF ABBREVIATIONS

ACIP	Advisory Committee on Immunization Practices
CBER	Center for Biologics Evaluation and Research
CDC	Centers for Disease Control and Prevention
EMR	Electronic medical record
FDA	Food and Drug Administration
GSK	GlaxoSmithKline Biologicals S.A.
HCP	Health Care Providers
HIPAA	Health Insurance Portability and Accountability Act
HMO	Health maintenance organization
ICD-9	International Classification of Diseases, Ninth Revision
ICD-10	International Classification of Diseases, Tenth Revision
IRB	Institutional Review Board
MAH	Market authorisation holder
MenACWY-CRM	Meningococcal ACWY vaccine conjugated to a carrier protein Cross reacting Material 197 (CRM 197)
PMC	Post-marketing commitment
PMS	Post-marketing study
KPSC	Kaiser Permanente Southern California
RIPC	Regional Immunization Practice Committee
RDW	Research Data Warehouse
SAE	Serious Adverse Event
SOP	Standard Operating Procedure
US	United States

3.4 Coordinating Investigator(s)

Not applicable.

3.5 CRO or Other Service Provider

Not Applicable.

3.6 Advisory Committee

Not Applicable

4.0 ABSTRACT

Name of Sponsor GlaxoSmithKline Biologicals S.A.	Protocol number: V59_74OB	Health authority study registration number(s):	Date of Protocol Abstract: 11AUG16
Title of Study: Post-licensure observational safety surveillance study of quadrivalent meningococcal ACWY conjugate vaccine MenACWY-CRM (MENVEO) among children 2 months through 23 months of age.			
Study Period: The study will start by December 2014 and data collection period will continue for 3 years.		Study Type: This study is an observational post-marketing safety study required by the United States Food and Drug Administration (FDA).	
Rationale and Background: Meningococcal disease is caused by Neisseria meningitidis . Multiple serogroups are responsible for invasive meningococcal disease (groups A, B, C, X, Y, and W-135). The relative importance of each serogroup depends on geographic location [1-5], as well as other factors, such as age. The overall incidence of meningococcal disease in the US during 2005-2011 has been approximately 0.3 cases per 100,000 population. [6] MenACWY-CRM (MENVEO) is a Meningococcal (Groups A, C, Y and W-135) Oligosaccharide Diphtheria CRM197 Conjugate Vaccine. The safety of Men ACWY-CRM has been evaluated in clinical trials in infants and toddlers 2 to 23 months of age. No safety concerns were raised.[7] In February 2010, MenACWY-CRM was approved for use in persons 11-55 years of age in the United States. As of August 2013 MenACWY-CRM was approved for use in persons 2 months through 55 years of age in the United States. In infants initiating vaccination at 2 months of age, MenACWY-CRM is to be administered as a four-dose series at 2, 4, 6, and 12 months of age. Among children 7-23 months of age who have not previously received a dose of MenACWY-CRM, MenACWY-CRM is to be administered as a two-dose series with the second dose administered in the second year of life and at least three months after the first dose. The Centers for Disease Control and Prevention's (CDC) Advisory Committee on Immunization Practices (ACIP) recommends the meningococcal conjugate vaccine MenACWY-CRM for use in infants			

Name of Sponsor GlaxoSmithKline Biologicals S.A.	Protocol number: V59_74OB	Health authority study registration number(s):	Date of Protocol Abstract: 11AUG16

and toddlers 2-23 months of age who are at increased risk for meningococcal disease.
 
This study will provide additional information to the current safety knowledge of MenACWY-CRM in the population 2-23 months of age.
			
Research Question and Objectives: To describe medical events that require emergency room visit or hospitalization in 6 months following MenACWY-CRM vaccination in children 2-23 months of age in a health maintenance organization (HMO) in the United States.			
Study Design: The study is a descriptive observational safety surveillance study. Medical events in emergency rooms and inpatient care units in children 2-23 months of age who were vaccinated with any dose of MenACWY-CRM vaccine will be described. Only medical events that occur within 6 months after a MenACWY-CRM vaccination will be captured. Events will be identified from electronic medical records of emergency care and inpatient care encounters. Medical records of these events will be reviewed and described.			
Population: Children 2-23 months of age who receive at least one dose of MenACWY-CRM vaccine at a Kaiser Permanente Southern California (KPSC) facility while enrolled as a KPSC health plan member.			
Variables: Exposure(s) of interest All administered doses of MenACWY-CRM at a KPSC facility are considered as exposures of interest in children 2-23 months of age who are KPSC members. The exposure of interest is MenACWY-CRM vaccine given as part of routine clinical care in all medical centers in KPSC. This study is strictly observational. MenACWY-CRM will be the only meningococcal vaccine used in children 2-23 months of age to prevent N. meningitidis serogroup A, C, W135 and Y caused meningococcal disease in KPSC.			

Name of Sponsor GlaxoSmithKline Biologicals S.A.	Protocol number: V59_74OB	Health authority study registration number(s):	Date of Protocol Abstract: 11AUG16
---	-------------------------------------	---	--

While health care providers (HCP) are advised to follow the ACIP Recommended Childhood Vaccine schedule, vaccination decisions will be determined by the treating HCP and the caregivers. MenACWY-CRM vaccine as a *N. meningitidis* A, C, W135 and Y vaccine will be used in infants and toddlers 2-23 months of age with high risk indications for the vaccine in KPSC. No special labeling will be required for the MenACWY-CRM vaccine used in this study. Co-administration of other vaccines may occur as consistent with clinical practice.

- Date (s) of MenACWY-CRM vaccination (s): exposure to MenACWY-CRM vaccination is defined as a registration of a MenACWY-CRM vaccination in the medical records. The date of vaccine administration in the medical records is considered as the vaccination date. Age at vaccination will be expressed in number of months after birth.
- Observation period: For each individual, the observation period is defined as the time from the first dose of MenACWY-CRM vaccination up to 6 months after the last dose of MenACWY-CRM vaccination received between 2-23 months of age, disenrollment, death, or the end of data collection, whichever occurs sooner.

Outcome(s)

Outcomes include medical events that require emergency room visits or hospitalizations in children 2-23 months of age following any dose of MenACWY-CRM vaccination. Events with a history of the same diagnosis prior to the first dose of MenACWY-CRM vaccination will be excluded as a pre-existing condition. The medical records prior to the first dose of MenACWY-CRM will be searched for the same diagnosis code.

For each identified emergency department or inpatient visit the following information will be collected:

- Diagnosis of medical events
- Date of diagnosis: the date of the documented code after any dose of MenACWY-CRM vaccination is considered the date of diagnosis. The date of diagnosis is expressed as the number of days following the 1st, 2nd, 3rd, or 4th dose of MenACWY-CRM vaccination.
- Health care setting: hospitalization or emergency room

Name of Sponsor GlaxoSmithKline Biologicals S.A.	Protocol number: V59_74OB	Health authority study registration number(s):	Date of Protocol Abstract: 11AUG16

Other Variables
 
 ▫ Baseline characteristics: these data will be extracted from patients’ medical records. 
 - Date of birth, expressed as age at vaccination - Gender ▫ Underlying condition of the MenACWY-CRM vaccine indication (i.e., persistent complement component deficiencies, asplenia or other), if available. ▫ Vaccination history 
 - Concomitant vaccinations (specify) - History of other vaccinations (specify) - Vaccinations occurring during the observation period (specify) 			

Data Sources:
 
Medical events occurring within 6 months following a MenACWY-CRM vaccination will be searched in electronic medical records from emergency care and inpatient care units. Vaccination information will be searched from vaccination records. Diagnoses occurring in any care setting (inpatient, outpatient, or emergency room) prior to the first dose of MenACWY-CRM vaccination will be searched in electronic medical records for evidence of pre-existing medical events.
			

Study Size:
 
There is no planned number of vaccinees. The study will include medically attended events that require an emergency room visit or hospitalization in the study population.
			

Data Analysis:
 
This study is descriptive in nature and there will be no hypothesis testing.
			

Informed Consent and Ethical Approval:
 
Subjects included in this study will be identified among KPSC health plan members. Informed consent for receipt of MenACWY-CRM vaccine is not required as it is given to eligible KPSC members as part of routine care. KPSC will obtain IRB approval and
			

Name of Sponsor GlaxoSmithKline Biologicals S.A.	Protocol number: V59_74OB	Health authority study registration number(s):	Date of Protocol Abstract: 11AUG16
will request waivers for both informed consent and written HIPAA authorization prior to initiating data collection.			
Milestones: Start of data collection: December 1, 2014 End of data collection: November 30, 2017 Final report of study results: November 30, 2018			

5.0 AMENDMENTS AND UPDATES

Number	Date	Section of the study protocol	Amendment or update	Reason
1	11AUG16	Throughout the text of this protocol.	Amendment	Main reason: To reflect the change of Sponsor from Novartis Vaccines and Diagnostics Inc. to GlaxoSmithKline Biologicals S.A.
1	11AUG16	Throughout the text of this protocol.	Amendment	Minor change: Name of the vaccine (MENVEO) has been capitalized.

6.0 MILESTONES

Milestone	Planned date
Start of data collection	December 1, 2014
End of data collection	November 30, 2017
Final report of study results	November 30, 2018

7.0 RATIONALE AND BACKGROUND

Meningococcal disease is caused by *Neisseria meningitidis*. Multiple serogroups are responsible for invasive meningococcal disease (groups A, B, C, X, Y, and W-135). The relative importance of each serogroup depends on geographic location, as well as other factors, such as age. Serogroup B and C strains are most prevalent in Europe, and serogroups B, C and Y strains are most prevalent in North America. Serogroup A strains are rarely isolated in Europe and North America. [1-5] The overall incidence of meningococcal disease in the US during 2005-2011 has been approximately 0.3 cases per 100,000 population. [6] Children younger than 1 year of age have the highest incidence of meningococcal disease in the United States.

MenACWY-CRM (MENVEO) is a Meningococcal (Groups A, C, Y and W-135) Oligosaccharide Diphtheria CRM197 Conjugate Vaccine. Safety of Men ACWY-CRM with 2-dose and 4-dose schedules has been primarily evaluated in multiple clinical studies in infants and toddlers 2 to 23 months of age. Serious adverse events (SAEs) were similar between the MenACWY-CRM and routine paediatric vaccination groups. Rates of severe unsolicited adverse events (AEs) reported in subjects who received MenACWY-CRM in co-administration with routine childhood vaccination and those who received routine childhood vaccination alone are similar. No vaccine related death was reported.[7]

In February 2010, MenACWY-CRM was approved for use in persons 11-55 years of age in the United States. As of August 2013 MenACWY-CRM was approved for use in persons 2 months through 55 years of age in the United States. In infants initiating vaccination at 2 months of age, MenACWY-CRM is to be administered as a four-dose series at 2, 4, 6, and 12 months of age. Among children 7-23 months of age who have not previously received a dose of MenACWY-CRM, MenACWY-CRM is to be administered as a two-dose series, with the second dose administered in the second year of life and at least three months after the first dose. The Centers for Disease Control and Prevention's (CDC) Advisory Committee on Immunization Practices (ACIP) recommends the meningococcal conjugate vaccine MenACWY-CRM for use in infants and toddlers 2-23 months of age who are at increased risk for meningococcal disease. Children at increased risk include those who have persistent complement deficiencies, have functional or anatomic asplenia, are at risk during a community outbreak attributable to a vaccine serogroup, or travel to or are residents of countries where meningococcal disease is hyperendemic or epidemic.[6]

The study is to be conducted in collaboration with Kaiser Permanente Southern California (KPSC) in the United States.

This study will add to the current knowledge about the safety of MenACWY-CRM in children 2-23 months of age in the setting of routine medical care.

8.0 RESEARCH QUESTION AND OBJECTIVES

To describe medical events that require an emergency room visit or hospitalization in 6 months following MenACWY-CRM vaccination in children 2-23 months of age in a health maintenance organization (HMO) in the United States.

9.1 RESEARCH METHODS

9.2 Study Design

This is a post marketing commitment (PMC) agreed upon with FDA Center for Biologics Evaluation and Research (CBER) to establish an open label, descriptive, epidemiological safety surveillance study of MENVEO in children 2 through 23 months of age who receive medical care at the site where the study is being conducted. Part I will continue for 3 years, or until commencement of Part II, whichever occurs first. Part II of the study will be initiated if there is a recommendation by the Advisory Committee on Immunization Practices (ACIP) for routine use of meningococcal conjugate vaccine in at least one birth cohort within the 2 through 23 months of age range.

Part II will commence with the effective date of the ACIP recommendation, and will continue until 20,000 children are enrolled, or until 1 year has elapsed, whichever occurs last. If initiated, a final study report for Part II will be submitted 1 year after the last subject has completed study Part II. In the event there is no recommendation for routine use of meningococcal conjugate vaccine in this age group, Part II will be considered fulfilled when Part I is completed.

This study protocol and timelines pertain only to Part I since there is currently no ACIP recommendation for routine use of meningococcal conjugate vaccine among children 2 through 23 months of age.

In Part I, medical events in emergency rooms and inpatient care units in children 2-23 months of age who were vaccinated with any dose of MenACWY-CRM vaccine will be described. Only medical events that occur within 6 months after a MenACWY-CRM vaccination will be captured. Events will be identified from electronic medical records of emergency care and inpatient care encounters. Medical records of these events will be reviewed and described.

9.3 Setting

The study will be conducted at Kaiser Permanente Southern California (KPSC), the largest managed care organization in Southern California, serving over 3.7 million members that are broadly representative of the diverse racial, ethnic and socioeconomic background of the source population in Southern California.[8] The racial/ethnic breakdown of the KPSC population is 41% Hispanic, 36% Non-Hispanic White, 11% Asian/Pacific Islander, 9% Black, and 3% other.

Prepaid, comprehensive health care is provided to KPSC members at 14 medical centers and over 200 satellite clinics. All health care encounters are tracked through electronic data systems, with detailed information on diagnoses applied, procedures performed, and

immunizations administered, regardless of setting. KPSC members may seek emergency medical care from outside health care providers. For outside providers to be reimbursed by the health plan for covered emergency care, claims have to be submitted with documentation of the episode of care, and that information is entered into the administrative data systems. Thus, the capture of care delivered to KPSC members by electronic data is very comprehensive.

KPSC health plan members can enroll through their employer or the employer of a family member, through individual and family plans, or through state or federal programs such as California Public Employees' Retirement System, MediCal, and Medicare.

The KPSC Regional Immunization Practice Committee (RIPC) makes recommendations to ensure appropriate use of vaccination and implementation of new ACIP immunization recommendations within KPSC. KPSC has a proactive immunization program that includes: 1) alerts in the electronic medical record that indicate which age-appropriate routine vaccines are due based on vaccines that the member has already received, 2) a policy of vaccinating at all visits, not just well child or physical exam appointments, and 3) giving immunizations on a walk-in basis without appointment and at no-cost nurse visits. Since there is no charge for immunizations for KPSC members, there is an incentive to receive immunizations within the KPSC system.

9.2.1 Study Period

The total study period will be up to 3.5 years, which includes vaccination period and observation period.

- Vaccination period will start at earliest in May 2014, and at latest in December 2014 to implement ACIP recommendation on preventing meningococcal serogroups A, C, W₁₃₅ and Y caused meningitis in persons aged 2 through 23 months.
- Observation period: For each individual, the observation period is defined as the time from the first dose of MenACWY-CRM vaccination up to 6 months after the last dose of MenACWY-CRM vaccination received between 2-23 months of age, disenrollment, death, or the end of data collection, whichever occurs sooner.

Pre-existing medical events will be assessed prior to the first dose of MenACWY-CRM vaccination.

9.2.2 Study Subjects

According to the ACIP recommended immunization schedule for persons aged 0 through 18 years, MenACWY-CRM is recommended for children 2-23 months of age with high-risk conditions and other persons at increased risk of disease. This population includes:

- children with anatomic or functional asplenia (including sickle cell disease)
- children with persistent complement component deficiency
- children who travel to or reside in countries in which meningococcal disease is hyperendemic or epidemic
- children at risk during a community outbreak attributable to a vaccine serogroup.

There are approximately 500,000 births per year in California,[9] equivalent to nearly 1 million infants and toddlers age 2-23 months. There were approximately 38,000 babies delivered at KPSC facilities and contracting hospitals in 2012.

There were approximately 122,000 infants and toddlers age 2-23 months enrolled in the KPSC health plan in 2013. Among this population, there were approximately 30 individuals diagnosed with sickle cell, asplenia, or persistent complement deficiency.

9.2.3 Study Population Selection

Children 2-23 months of age who receive at least one dose of MenACWY-CRM vaccine at a KPSC facility while enrolled as a KPSC health plan member are considered as the study population.

Inclusion criteria:

- children 2-23 months of age at the time of MenACWY-CRM vaccination
- hold KPSC membership at the time of MenACWY-CRM vaccination
- vaccinated with MenACWY-CRM during the study period in KPSC

There are no exclusion criteria for selection of the study population.

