9.4.2 Operational Outcome Definition and Identification Process

Medical events occurring in emergency and inpatient settings within 6 months following a MenACWY-CRM vaccination will be searched in electronic medical records. Diagnoses occurring in any care setting (inpatient, outpatient, or emergency room) prior to the first dose of MenACWY-CRM vaccination will be searched in electronic medical records for evidence of pre-existing medical events.

Events with a history of the same diagnosis prior to the first dose of MenACWY-CRM vaccination will be excluded as a pre-existing condition. The medical records prior to the first dose of MenACWY-CRM will be searched for the same diagnosis code. As there will be a transition from International Classification of Diseases, Ninth Revision (ICD-9) to Tenth Revision (ICD-10) coding, in the event that the diagnosis following a MenACWY-CRM vaccination is coded using ICD-10, both the same ICD-10 code and an equivalent ICD-9 diagnosis code will be searched in the period prior to the first dose.

If a study subject is first seen in the emergency department and subsequently transferred to the hospital, this will be treated as a single episode of care. Multiple records of a single medical event will be consolidated and treated as 1 report.

Medical events are considered as eligible if they occur in eligible study subjects during the observation period and are not pre-existing conditions.

For each identified emergency department or inpatient visit the following information will be collected:

[figure not shown]
- Diagnosis of medical events
- Date of diagnosis: the date of the documented code after any dose of MenACWY-CRM vaccination is considered the date of diagnosis. The date of diagnosis is expressed as the number of days following the 1st, 2nd, 3rd, or 4th dose of MenACWY-CRM vaccination.
- Health care setting: hospitalization or emergency room visit

Process of medical events identification

Eligible medical events identification process is illustrated in Figure 1:

1. Children 2-23 months of age vaccinated with MenACWY-CRM will be identified by immunization records in electronic medical records.
2. Medical events will be searched up to 6 months following MenACWY-CRM vaccination in the electronic records of emergency department and inpatient care units in all medical centers of KPSC.
3. Diagnosis codes of medical events from these visits will be identified.

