9.8 Quality Control

9.8.1 Validation

Vaccination and medical event data will be extracted directly from the electronic medical record, which is the legal record of all medical care received within the KPSC system. Records of vaccinations and medical events can only be entered by medical staff, and are assumed to be an accurate representation of care received. No validation will be performed regarding vaccination. Medical events will be individually reviewed in order to determine the primary reason for the encounter as well as whether the condition predated the first receipt of MenACWY-CRM.

All data in the study is extracted and maintained in the electronic database at KPSC. The database is maintained on a daily basis, and undergoes quality validations regularly. Only authorized study personnel with passwords can access to databases. Validations of data in the study database will include range and consistency checks.

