5.1 Identification and review of events

Medical events occurring in ED and inpatient settings within 6 months following a MenACWY-CRM vaccination will be searched in the EMR.

Medical events will be characterized two ways: by encounter (hospitalization only, ED only, or both ED and hospitalization) and by diagnosis (see Appendix A, Table Shell 4 for details). The analysis allows for any recurrent events (i.e. different episodes of the same diagnosis) to be counted independently.

For characterization by encounter (Table 4a), all dates used for analysis will be the date of the ED encounter or hospital admission. Encounters will be considered pre-existing if all diagnoses made during the encounter are present in the medical record prior to the first dose of vaccine. Upon chart review by the study physician co-investigator, an encounter will be refuted if it is found to not be a true ED or hospital encounter. Each encounter will be reported as a single event, regardless of the number of diagnoses made during the encounter.

For characterization by diagnosis (Table 4b), all dates used for analysis will be the first date that the diagnosis is recorded in the EMR in any medical setting. A diagnosis will be excluded as pre-existing if the same ICD diagnosis code appears in any medical setting prior to the first dose of MenACWY-CRM vaccination. A diagnosis will be considered refuted if, upon chart review by the study physician co-investigator, there is no evidence of the diagnosis in the medical record. Multiple diagnoses associated with the same episode will be identified, but only the first diagnosis date (in any setting) will be counted in the analysis of each episode. Subsequent diagnoses for the same episode will be marked in Table 4b as “Diagnosis is continuation of an ongoing episode.” An episode will be considered as ended when there is symptom resolution as determined by chart review (e.g., symptoms stated to have resolved or the diagnosis/symptoms have been absent from the medical record before they are mentioned again). In the case of recurrent events, the date used will be the date of the first diagnosis in the medical record following resolution of the prior episode. Recurrent events will be marked in Table 4b as “Diagnosis is a recurrence”. Each diagnosis will be described independently. It is possible that different diagnoses from the same inpatient or ED encounter could have different diagnosis

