5.4 Sensitivity analysis

No sensitivity analyses are planned.

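### With no minimum prior membership, excluding pre-existing conditions in recent KPSC joiners rests on chart review, so some can be counted as new post-vaccination diagnoses

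*Protocol*

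**What the plan says.** Protocol 9.2.3 admits children who "hold KPSC membership at the time of MenACWY-CRM vaccination" and adds: "There are no exclusion criteria for selection of the study population". Neither the protocol nor the SAP asks for any membership before that date.

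Pre-existing conditions are removed in two steps.

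- **Automated search.** Protocol 9.4.2: "The medical records prior to the first dose of MenACWY-CRM will be searched for the same diagnosis code". SAP v2.0, section 5.1: "A diagnosis will be excluded as pre-existing if the same ICD diagnosis code appears in any medical setting prior to the first dose". No look-back length is set. The same SAP section dates a diagnosis by its first appearance in the KPSC electronic record.
- **Chart review.** Protocol 9.8.1 has each event reviewed for the main reason for the encounter, "as well as whether the condition predated the first receipt of MenACWY-CRM". Column (f) of Tables 4a and 4b holds confirmed events found to predate the index dose, and both tables subtract it from the total analysed.

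On limitations, Protocol 9.7.4 and SAP 6.2 accept that vaccine doses given before joining may be missed. For missed pre-existing conditions they name only imperfect ICD-9 to ICD-10 mapping. SAP 5.4: "No sensitivity analyses are planned".

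**The concern.** The automated step treats the absence of a KPSC code as the absence of a history. That is reasonable for a child enrolled since birth. It is weak for a child who joins at, say, 11 months and is vaccinated a week later: the record is nearly empty, and the first emergency visit for an older condition passes the search with a date after the dose.

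The study has no comparator that would show such inflation. SAP 3.2 expects only about 60 to 100 high-risk children, and Table 6 describes any diagnosis that reaches five episodes, so a few misplaced events can change what is reported. The plan recognises the problem of care before joining for vaccine doses, but does not carry the reasoning over to diagnoses.

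**Working it through.** **Path of one event.** Take a recent joiner with an older condition that has no KPSC code before dose 1.

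1. Eligibility: met, since membership on the vaccination date is enough.
2. Automated search: no earlier code, so the diagnosis is not removed in column (b).
3. Dating: the first KPSC entry falls after the dose.
4. Chart review: the event is removed in column (f) if the chart shows that the condition is older. SAP 5.1 defines when a diagnosis is refuted but gives no rule for column (f). Protocol 9.8.1 describes the record as covering care within the KPSC system. The outside-claims route in the Setting section of the Protocol concerns members' emergency care. Nothing describes capture of care before joining.
5. If the chart is silent, the event enters Table 5b as a new diagnosis. Table 5a is less exposed: an encounter is pre-existing only if all its diagnoses are, so one new code keeps it in whether or not the history is complete.

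**How many children might be affected?** The documents do not say. The nearest figures are in Protocol 9.2.2 ("There were approximately 38,000 babies delivered at KPSC facilities and contracting hospitals in 2012", and some 122,000 members in the age band in 2013) and Protocol 9.5 (about 245,000 aged 2-23 months enrolled over 2011 to 2013). Assume a constant 38,000 deliveries a year, and that the enrolment figures count everyone in the age band at some time in the period. The 22-month band plus the period gives the span of birth months.

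- 2013: 22 + 12 = 34 months. 38,000 × 34/12 = 107,667. Gap: (122,000 − 107,667)/122,000 = 11.7%.
- 2011 to 2013: 22 + 36 = 58 months. 38,000 × 58/12 = 183,667. Gap: (245,000 − 183,667)/245,000 = 25.0%.

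So roughly 12% to 25% of enrolled children were not delivered at KPSC. Many of these may have been enrolled since early infancy, so this is not the share with a short look-back.

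**What it could do to a rate (illustration).** Let s be the share of vaccinees with a short look-back, m the existing-condition events that pass the search per truly new event in those children, and c the fraction removed at review. With equal person-time and equal true rates in both groups, relative inflation = s × m × (1 − c). None of the three is in the documents. Assume s from 5% to 25% and m from 0.25 to 1.

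- c = 0: 0.05 × 0.25 = 1.25%, up to 0.25 × 1 = 25%.
- c = 0.8: multiply by 0.2, giving 0.25% to 5%.
- c = 1: zero.

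**Against the plan's own precision.** SAP 3.2 gives 81.4-121.6 for 100 events per 100 person-years and N = 100. The exact Poisson interval for 100 events in 100 person-years is 81.36 to 121.63, which reproduces it. An inflation of 10% (for example s = 20%, m = 0.5, c = 0) gives 110 events and an interval of 90.4 to 132.6. The shift lies within the sampling error of the overall rate, but can matter more for an individual diagnosis.

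**The case against.** The strongest reply is that the automated search is not the last filter. A reader might infer from the eligibility rule that existing conditions in recent joiners are simply counted as new. The documents do not support that: Protocol 9.8.1 sends each event to individual review on exactly this question, SAP 3.1 has a physician review all identified events, and column (f) is subtracted. Nothing shows how often review would fail. This stands, and it limits the point to a residual bias. It does not remove the point, because review draws on the same possibly sparse chart.

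Three other inferences also go too far.

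- **That up to 43% of children are new joiners.** Reading 122,000 as a point count gives 38,000 × 22/12 = 69,667 and a gap of 43%. But a point count would imply about 122,000/22 × 58 = 321,600 children over 2011 to 2013, against the stated 245,000. Read as a count over the year, it implies 122,000/34 × 58 = 208,100, which turnover could bring up to 245,000. Under either reading the gap measures place of delivery, not length of membership.
- **That the split into first occurrence and recurrence is wrong.** A diagnosis with earlier history is to be excluded, not classed as a recurrence; SAP 5.1 uses recurrence for a new episode after an earlier one has resolved. A missed history leaves an event wrongly included.
- **That the whole cohort has lasting disease.** Protocol 9.2.2 also lists travel, residence abroad and outbreaks. Where a lasting condition is the reason for vaccination, KPSC probably knows of it by dose 1; that is inference.

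It is also fair to say that a subset analysis in so small a cohort will be imprecise.

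**Conclusion.** The point holds as a cheap improvement. No prior membership is required, the automated search has no minimum look-back, and for recent joiners the exclusion of existing conditions therefore rests on chart review of a record that may hold little from before membership. Some existing conditions can be counted as new post-vaccination diagnoses, mainly in Table 5b, and the plan neither names this limit nor provides a way to see it.

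The direction is upward. The size is unknown: under the assumed ranges it runs from zero, if review catches everything, to about 25% if it catches nothing and both the share of recent joiners and their burden of older conditions are at the top of the range. The 12% to 25% of children not delivered at KPSC is background only and should not be quoted as the share affected.

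**What to change.** - Keep all children; do not add a membership criterion. A fixed minimum would not suit infants vaccinated at 2 months.
- Derive months of continuous KPSC membership before dose 1 and report them in Table 2. SAP 9.1 already lists membership among the study data.
- Replace SAP 5.4 with one sensitivity analysis: repeat the overall columns of Table 5b, and of Table 5a, in children continuously enrolled from within the first month of life to dose 1.
- State in SAP 6.2 that diagnoses made before joining KPSC may be missed, alongside the existing sentence on vaccine doses.
- Do not relabel every other child's diagnoses as having unobservable prior history. Many of those children will have months of usable records.

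If SAP 5.1 is being edited anyway, a sentence on how column (f) is decided would help, though the point does not depend on it.

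The cost is SAP wording, one added table row and one rerun of existing programs on a subset. The downside is precision: in the SAP's own table, going from N = 100 to N = 50 at 100 events per 100 person-years widens the interval from 81.4-121.6 to 74.2-131.8. The subset result should be read as a check on direction, not as a second estimate.
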